8.5.3 Exploratory Analyses

Pharmacokinetics parameters for CT-P27 components (CT-P22 and CT-P23) will be summarized at each dose level (45 mg/kg and 90 mg/kg) using descriptive statistics. Summary statistics will include the number of observations (n), mean, SD, median, minimum, maximum, geometric mean, and coefficient of variation (CV%). All PK analyses will be based on the PK population. Dose proportionality for CT-P22 and CT-P23 will be assessed. Details are provided below.

Serum concentrations will be summarized by treatment group at each scheduled collection time as specified in [Table 1](#). In addition to the standard summary statistics (n, mean, SD, median, minimum, and maximum), the geometric mean and CV% will also be presented at each time point. Mean serum concentration-time profiles of study drug will be plotted by treatment on linear and semi-logarithmic scales based on scheduled sample times. Individual concentrations and scheduled and actual sample times will be presented in data listings by treatment. Individual linear and semi-logarithmic concentration-time plots (based on scheduled sample times) with respective treatments presented together will also be included. For the calculation of PK parameters, all serum concentrations that are below the limit of quantitation (BLQ) prior to the first measurable concentration will be set to zero. The BLQ values after administration of study drug will be set equal to the lower limit of quantification.

The following PK parameters will be calculated using non-compartmental methods for CT-P22 and CT-P23:

- AUC_{0-last} calculated using the linear trapezoidal rule. This will be calculated over the study period.
- C_{max} obtained directly from the observed concentration versus time data.
- $AUC_{0-\infty}$ calculated using the linear trapezoidal summation and extrapolated to infinity by addition of the last quantifiable concentration divided by the terminal rate constant: $AUC_{0-last} + C_{last}/\lambda_z$.
- t_{max} obtained directly from the observed concentration versus time data.
- C_{last} obtained from the last observed quantifiable concentration.

- λ_z determined by linear regression of the terminal points of the log-linear concentration-time curve. Visual assessment will be used to identify the terminal linear phase of the concentration-time profile.
- $t_{1/2}$ determined as $\ln 2/\lambda_z$.
- MRT, determined as $AUMC_{0-\infty}/AUC_{0-\infty}$, where $AUMC_{0-\infty}$ is the area under the first-moment curve evaluated from time zero to infinite time.
- CL calculated as the administered dose divided by $AUC_{0-\infty}$.
- V_z calculated as $Dose/(\lambda_z \cdot AUC_{0-\infty})$, where dose is the IV dose.

The following PK parameters will be calculated for diagnostic purposes and listed, but will not be summarized:

$t_{1/2}$, Interval	The time interval (hour) of the log-linear regression to determine $t_{1/2}$.
$t_{1/2}$, N	Number of data points included in the log-linear regression analysis to determine λ_z . A minimum of 3 data points will be used for determination.
Rsq	Coefficient of determination for calculation of λ_z . λ_z and related parameters will be listed and not summarized if Rsq is less than 0.800.
%AUC _{ex}	Percentage of $AUC_{0-\infty}$ obtained by extrapolation, calculated as $[(C_{last}/\lambda_z)/AUC_{0-\infty} \times 100]$. If the extrapolated area (C_{last}/λ_z) is greater than 30% of $AUC_{0-\infty}$, then $AUC_{0-\infty}$ and related parameters will be listed and not summarized.

For the calculation of PK parameters, pre-dose samples that are BLQ or missing will be assigned a numerical value of zero for the calculation of the AUC. Any anomalous concentration values observed at pre-dose will be identified in the study report and used for the computation of AUC. PK parameters will be computed if the anomalous value is not greater than 5% of the C_{max} . If the anomalous value is greater than 5% of C_{max} , only the concentration values will be listed and no PK parameters will be calculated or analyzed.

PK parameters will be summarized by treatment group. Summary statistics will include n, mean, SD, median, minimum, maximum, geometric mean, CV%.

Dose proportionality for CT-P22 and CT-P23 will be assessed for C_{max} and AUC_{0-last} using the Power model. For each of the parameters assessed, a plot of the log-transformed parameter value against the log-transformed dose will be constructed including the fitted line from the

linear regression and the line of unity slope. The 95% confidence interval (CI) or P-value for the slope will be presented.

Immunogenicity will be assessed in the safety population by baseline and post-treatment serum measures of anti-CT-P27 component antibodies, CT-P22 and CT-P23 antibodies, using immunoassay. These data will be summarized by treatment groups and time point.

Genotype and phenotype analysis will be assessed in the ITTI population by baseline and post-treatment virus measures.

In addition, changes in HI antibody will be assessed in the PK population and summarized by treatment group and time point.

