6.3 Exploratory Assessments

A PK sub-study will only be performed on the subjects who signed additional informed consent to participate in a PK sub-study. Blood sampling for PK analysis will be collected from subjects on Day 1 at pre-infusion (within 15 minutes prior to the beginning of the infusion), the end of infusion (within 15 minutes after the end of the infusion), 1 hour (± 15 minutes) after the end of the infusion, and then on Day 2 (24 hours [± 4 hours] after the start of the study drug infusion), Day 3 (48 hours [± 4 hours] after the start of the study drug infusion), Day 8 (168 hours [± 4 hours] after the start of the study drug infusion), Day 15 (± 2 days), Day 29 (± 5 days), Day 57 (± 5 days), and Day 110 (± 5 days)/EOS visit.

Samples taken on Day 1 will be collected in the opposite arm from that being used for the IV infusion of study drug. The date and time of collection of each sample and any missing blood draws will be recorded in the respective eCRF. Samples will be collected, labeled, stored, and shipped as detailed in the Laboratory Manual.

Bioanalysis will be carried out for the simultaneous determination of CT-P22 and CT-P23 using a validated ligand binding assay. Bioanalysis will be carried out at the bioanalytical site. Contact details for the bioanalytical site are available in Table 4.

Blood will be drawn at Day 1 (before study drug administration) and Day 110/EOS visit to evaluate the immunogenicity of CT-P27 components, CT-P22 and CT-P23. Samples will be secured at the central laboratory for immunogenicity analysis and backup samples will be retained.

For the subjects with Influenza A confirmed by qPCR or cell culture, genotypic analysis on HA and NA genes, and phenotype characterization of potential escape variants with regard to CT-P27 will be evaluated using the nasopharyngeal swab samples. Samples will be secured at the central laboratory for analysis and backup samples will be retained.

In addition, blood samples will be taken at Day 1 (at pre-infusion) and Day 29 (± 5 days)/EOS visit (if a subject is early terminated from the study) to determine HI antibody in Subgroup (PK) Cohort.

Primary samples will be secured at the central laboratory for PK, immunogenicity of CT-P22 and CT-P23, and HI antibody analysis and backup samples will be retained. Back-up samples will be retained up to 5 years after the end of the study unless a specific authorization is

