8.2.4 Exploratory Endpoints

Blood sampling for PK analysis will be collected from the subjects on:

- Day 1 at pre-infusion (within 15 minutes prior to the beginning of the infusion), the end of infusion (+15 minutes), 1 hour (± 15 minutes) after the end of the infusion,
- Day 2 (24 hours [± 4 hours] after the start of the study drug infusion),
- Day 3 (48 hours [± 4 hours] after the start of the study drug infusion),
- Day 8 (168 hours [± 4 hours] after the start of the study drug infusion),
- Day 15 (± 2 days), Days 29, 57 and 110 (± 5 days) or at end of study visit (EOS visit).

Blood sampling for Immunogenicity assessment will be collected on Day 1 (at pre-infusion) and Day 110 (± 5 days) or EOS visit.

For the subjects with Influenza A confirmed by qPCR or cell culture, genotypic analysis on HA and NA genes, and phenotype characterization of potential escape variants with regard to CT-P27 will be evaluated using the nasopharyngeal swab samples.

Blood sampling for assessment of anti-influenza antibodies (Hemagglutination inhibition) will be collected on Day 1 (at pre-infusion) and Day 29 (± 5 days) or EOS visit (if a subject is early terminated from the study) in Subgroup (PK) Cohort.

Additional genotyping tests could be conducted if it is required from a regulatory or medical perspective.

The following parameters are determined as exploratory endpoints:

- PK profiles
 - $AUC_{0-\infty}$: Area under the concentration-time curve in serum from time zero extrapolated to infinite time
 - AUC_{0-last} : Area under the concentration-time curve from time zero to the last quantifiable concentration
 - C_{max} : Maximum observed serum concentration
 - t_{max} : Time of maximum concentration
 - C_{last} : Last observed quantifiable concentration
 - λ_z : Apparent terminal elimination rate constant

- $t_{1/2}$: Apparent terminal elimination half-life
 - MRT: Mean residence time
 - CL: Systemic clearance from serum after IV dosing
 - V_z : Apparent volume of distribution during the terminal elimination phase after IV dosing
- Anti-drug specific antibodies for CT-P27 component antibodies (CT-P22 and CT-P23)
 - HI antibody.
 - Genotype and phenotype of isolated influenza virus

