11.2 Immunogenicity Analysis

Immunogenicity will be assessed in the safety population by baseline and post-treatment serum measures of anti-CT-P27 component antibodies, CT-P22 and CT-P23 antibodies, using immunoassay. Immunogenicity assessments consist of both Anti-Drug Antibody (ADA) and Neutralizing Antibody (NAb) assays. The ADA

Statistical Analysis Plan

assay will follow a three-tiered approach consisting of (i) screening assay, (ii) specificity/confirmatory assay, and (iii) titration. The test outcome for the screening assay will be: {"Potential Positive" or "Negative"}. Samples that are "Potential Positive" in the screening assay will be undergone further testing in the specificity/confirmatory assay to determine if subjects are a true positive. The test outcome for the specificity/confirmatory assay will be: {"Reactive", "Negative", and "Not applicable (N/A)"}. "Reactive" indicates a true positive test outcome, "Negative" is considered negative and "N/A" indicates the assay was negative at the screening phase of the process. Subjects with a "Negative" test outcome for either screening or specificity/confirmatory assays will be considered negative for the overall ADA assessment. For further characterization, quantitative antibody level will be assessed by titration in confirmed positive samples. The ADA value of the CT-P22 and CT-P23 tagged assay will be transformed using a log transformation. Transformed ADA value can be obtained using $[\log_2(X/20)] + 1$ transformation.

Samples that are positive in the assessment will be analyzed further to conduct a NAb assessment. The same three-tiered approach of ADA assay will be applied to NAb assay. Transformed NAb value can be obtained using $[\log_2(X/10)] + 1$ transformation. If ADA or NAb titer values in the data are in inequality forms, the sign of inequality will be removed and then the values will be transformed.

Immunogenicity result for CT-P22 and CT-P23 are listed and summarized separately. The number and percentage of subject will be presented by treatment group and test at each scheduled time point for the safety population.

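### Anti-drug and neutralising antibody are tabulated only as the percentage positive at each time point, so antibody newly induced by CT-P27 is not separated from reactivity already present before dosing

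*Protocol*

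**What the plan says.** Assessing immunogenicity is an exploratory objective (protocol 3.3, SAP 2.3). Protocol 8.2.4 sets two sampling times: "Blood sampling for Immunogenicity assessment will be collected on Day 1 (at pre-infusion) and Day 110", or the end-of-study (EOS) visit. Protocol 8.5.3 states the measure, "Immunogenicity will be assessed in the safety population by baseline and post-treatment serum measures of anti-CT-P27 component antibodies", and then the summary: "These data will be summarized by treatment groups and time point".

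SAP 11.2 adds the assay detail. ADA goes through screening, confirmation and titration, and ADA-positive samples go on to an NAb assay. A sample is positive or negative on its own screening and confirmatory result. Further, "quantitative antibody level will be assessed by titration in confirmed positive samples", and ADA and NAb titres are put on a log2 scale. On output, the SAP says "Immunogenicity result for CT-P22 and CT-P23 are listed and summarized separately" and "The number and percentage of subject will be presented by treatment group and test at each scheduled time point for the safety population".

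The table list in SAP 14.7 has one immunogenicity table, 14.2.22, of which only the title is shown, and two listings, 16.2.6.8.1 and 16.2.6.8.2. Neither document defines treatment-induced or treatment-boosted antibody, plans a shift table for ADA or NAb, or describes any summary of titre or of its change from baseline.

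**The concern.** The purpose of a pre-dose sample is to tell antibody that arose after the drug from reactivity that was there before it. The planned summary does not use the sample in that way: it reports two separate percentages per arm. A subject reactive before dosing and again at Day 110 adds to the Day 110 percentage just as a newly reactive subject does. A subject who turns from reactive to negative offsets a newly reactive one when the two percentages are compared.

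At stake is the immunogenicity description for each dose. The Day 110 percentage can overstate induced antibody, and the change from the baseline percentage can understate it.

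The SAP links post-dose to baseline results elsewhere. HI antibody in 11.3.1 has fold rise over baseline and responder categories based on the baseline titre. Shift tables are planned for physician assessment, laboratory results, ECG, physical examination and chest X-ray.

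**Working it through.** The documents give no rate or sample size for immunogenicity, so there is no figure to reproduce. The check is of what the planned summary can identify. The arm sizes of 70 and 43 are from protocol 4.1; every rate below is an assumption.

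**1. The two percentages do not determine the incidence.** Take one CT-P27 arm of 70, all with both samples, with 4/70 (5.7%) positive at baseline and 4/70 (5.7%) at Day 110. There are 70 − 4 = 66 baseline-negative subjects.

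| Positive at both times | New positives | Incidence in baseline negatives |
|---|---|---|
| 4 | 0 | 0/66 = 0% |
| 3 | 1 | 1/66 = 1.5% |
| 2 | 2 | 2/66 = 3.0% |
| 1 | 3 | 3/66 = 4.5% |
| 0 | 4 | 4/66 = 6.1% |

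The by-time-point percentages are the same in all five rows. A cross-tabulation tells them apart.

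**2. How far the percentages can drift.** Let b be baseline prevalence, s the share of baseline positives still positive at Day 110, and i the incidence among baseline negatives. Then

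Day 110 percentage D = b·s + (1 − b)·i.

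With i = 2% and s = 80%:

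- b = 2%: D = 1.60 + 1.96 = 3.56%; D − b = +1.56 points
- b = 5%: D = 4.00 + 1.90 = 5.90%; D − b = +0.90 points
- b = 10%: D = 8.00 + 1.80 = 9.80%; D − b = −0.20 points

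Over b = 0–10%, i = 0–5% and s = 50–100%, D runs from 0% to 14.5%. With i = 0 and s = 100%, D still reads 5% at b = 5% and 10% at b = 10%. With b = 10%, s = 50% and i = 5%, D = 5.0 + 4.5 = 9.5%, a net change of −0.5 points despite a true incidence of 5%. With b = 0, D = i and there is no distortion.

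**3. What the placebo arm recovers.** Assume no new reactivity on placebo and the same b and s in each arm. Placebo at Day 110 is then b·s = 1.60, 4.00 and 8.00%. The CT-P27 minus placebo difference is 3.56 − 1.60 = 1.96, 5.90 − 4.00 = 1.90 and 9.80 − 8.00 = 1.80 points. This equals (1 − b)·i, so dividing by 1 − b returns 2% in each case.

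**4. Precision of that contrast.** At b = 5%, with 70 and 43 subjects, its standard error is √(0.059·0.941/70 + 0.040·0.960/43) = √(0.000793 + 0.000893) = 0.041, or 4.1 points. Counting new positives among the expected 70·0.95 = 66.5 baseline negatives gives √(0.02·0.98/66.5) = 0.017, or 1.7 points. These are rough normal-approximation figures at low rates, but the ordering is clear.

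**The case against.** Several points on the other side stand.

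- **No carry-forward.** A reader might infer that antibody present at baseline is automatically counted as positive at Day 110. There is no such rule. Each sample is classified on its own assay result, so a baseline-positive subject counts at Day 110 only if reactive again then. The table would report prevalence correctly, and neither document calls it incidence.
- **Incidence is not out of reach.** A reader might infer that it cannot be obtained. The listings hold each subject's results and, by the SAP 5.1 default, sort by treatment group, subject number and date. With two scheduled samples each in about 183 subjects, conversions can be read off. What is missing is a planned tabulation and a definition fixed in advance.
- **The placebo arm helps.** The table is by treatment group, and step 3 shows that the randomised contrast comes close to the incidence on average. It is noisier, and it relies on similar baseline reactivity and persistence across arms.
- **Importance is limited.** The endpoint is exploratory and no test or decision rests on it. The inputs named for dose selection in protocol 2.2 and SAP 1.1 do not include immunogenicity. Protocol 2.4.1 reports very low immunogenicity so far. That reduces the likely count of induced cases but says nothing about reactivity before dosing; when induced cases are few, a handful of pre-existing reactors can make up much of the Day 110 count.
- **Table content is not visible.** Only the title of Table 14.2.22 is shown. The reading here rests on the text of SAP 11.2, which describes no linked result.

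**Conclusion.** The point holds as a gap in the planned summary. SAP 11.2 and protocol 8.5.3 specify point prevalence of ADA and NAb at baseline and at Day 110; treatment-induced and treatment-boosted antibody are neither defined nor tabulated. Two marginal percentages cannot identify new antibody once anyone is reactive before dosing, and this does not depend on the assumed rates.

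The size does depend on them. In the illustration with 2% incidence and 80% persistence, the Day 110 percentage alone is 1.8 to 4.9 times the incidence for baseline reactivity of 2% to 10% (3.56/2 to 9.80/2). That ratio should not be read as the error in the trial's conclusions, because it sets aside the placebo arm. The documents give no baseline reactivity, and the distortion is zero if it is zero. This is a worthwhile low-cost improvement to an exploratory endpoint and does not affect the efficacy analyses.

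**What to change.** In SAP 11.2 and Table 14.2.22, by arm including placebo, for CT-P22 and CT-P23 and for ADA and NAb, add:

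- a baseline-by-post-dose cross-tabulation of positive and negative results;
- **treatment-induced** antibody: negative at baseline and confirmed positive post-dose, with baseline-negative subjects who have a post-dose result as denominator. Dividing by all subjects with paired samples would give 1.96/1.90/1.80% in the illustration, not the 2% incidence among those at risk;
- **treatment-boosted** antibody: positive at baseline with a titre rise above a threshold fixed before unblinding, with baseline-positive subjects who have a post-dose result as denominator. A rise of at least 2 on the SAP's log2 scale, which is 4-fold, is one example. The documents give no assay-variability data to support a particular cut-off, so the sponsor should justify the choice.

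State the denominators explicitly, because the SAP 5.1 default is everyone in the arm and population, which includes subjects with no Day 110 sample. State also that an ADA-negative sample counts as NAb-negative, since only ADA-positive samples are tested for NAb. Include post-dose samples from early-termination visits, which SAP 5.1 otherwise leaves out of the EOS summary and shows only in listings. Keep the by-visit rows.

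The cost is a paragraph of SAP text and a few table rows. No new samples, visits or assays are needed.

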8.5.4 Safety Analyses

The safety analysis will be performed on the safety population at the time points specified in [Table 1](#) by presenting data on TEAEs, TESAEs, TEAEs leading to treatment discontinuation, clinical laboratory analyses, vital signs, ECG, physical examination, suspicious ADE, and other safety evaluations.

8.5.4.1 Adverse Events

Adverse events will be graded for severity and the terminology of AEs will be described according to the CTCAE v4.03. All safety data will be listed and summarized by treatment group as appropriate.

Adverse events will be coded to system organ class (SOC) and preferred term (PT) according to MedDRA.

The following TEAE summaries will be reported by SOC, PT, and treatment group:

- Number and percentage of subjects reporting at least one TEAE by SOC and PT
- Number and percentage of subjects reporting at least one TESAЕ by SOC and PT
- Number and percentage of subjects reporting at least one TEAE leading to treatment discontinuation by SOC and PT

Treatment-emergent AEs will also be summarized by maximum severity and relationship to study drug with the percentage of subjects in each category. If more than one TEAE is recorded for a subject within any SOC or PT, the subject will only be counted once using the most severe assessment.

The number and percentage of subjects with suspicious TEADE will be presented by treatment group.

8.5.4.2 *Clinical Laboratory Evaluations*

Clinical laboratory tests (hematology, biochemistry, and urinalysis) will be summarized, by treatment, at each scheduled collection time. For continuous parameters, change from baseline will also be summarized for all scheduled collection times after the first infusion. Clinical laboratory data will also be summarized using shift tables for categorical parameters.

All laboratory results will be listed.

8.5.4.3 *Vital Signs Measurements, Physical Findings, and Other Safety Evaluations*

Vital signs of SBP, DBP, heart rate, and respiration rate will be summarized by treatment group, at each scheduled collection time. Changes from baseline will also be summarized by treatment group.

The number and percentage of subjects with abnormalities in vital signs or ECG during the infusion and immediate post-infusion period will be summarized by time point and treatment group.

Physical examination results will be summarized by counts and percentages at each scheduled collection time. In addition, shift tables will be presented.

Electrocardiogram parameters will be summarized by counts and percentages, at each scheduled collection time. In addition, shift tables will be presented.

8.5.5 *Subject Baseline Characteristics*

Demographics (age, sex, and race) and other background characteristics such as medical history will be presented in summary tables for the ITT population and ITTI population. Qualitative data will be summarized in contingency tables, and quantitative data will be summarized using quantitative descriptive statistics.

8.6 *Data to be Analyzed*

The data will be inspected for inconsistencies by performing validation checks.

All details regarding the statistical analysis and the preparation of tables, listings, and figures will be described in the SAP before database lock.

